12.5. Protocol Deviations

Important Protocol Deviations will be summarized. The MEDIcept team will identify important protocol deviations and will be reviewed prior to database lock.

12.6. Subject Disposition

Subjects who have signed the Informed Consent Form with available data for the will be used in the statistical analysis, i.e., a complete case analysis, for Per Protocol analysis. All subjects will be included in the Intent to Treat (ITT) analysis.

12.7. Demographics

Subject demographics will be summarized using descriptive statistics (mean, median, Standard Deviation (SD), minimum, maximum), number of subjects for continuous variables (e.g., age), and frequency distributions (number and percentage of subjects) for categorical variables (e.g., sex at birth, race, and ethnicity).

12.8. Safety

All adverse events for participants in the safety population will be reported.

- Serious Adverse Events
- Non-serious Adverse Events Device Related Adverse Event
- Device Related Serious Adverse Events

Results will include the number of participants experiencing each type of event as well as the number of events.

12.9. Concomitant Medication

All concomitant medication for pain will be recorded. A medication is considered concomitant if the start date is before the informed consent and there is no stop date, or the stop date is after the end of study treatment.

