8.5 Exclusion Criteria

Participants must not meet ANY of the following criteria:

1. Have a cardiac pacemaker, cardioverter defibrillator, neurostimulator, infusion pump or any active medical implant
2. Have an implanted metallic lead or any type of wire coil implant, or any implanted system that may contain lead
3. Current or expected use of opioids
4. Who are or may be pregnant
5. Have an open wound at the area of application
6. Are not capable or fully aware to the sensation of heat
7. Have poor circulation or heart disease
8. Have diabetes
9. Under the age of 18 or individuals with open bone growth plates
10. Unable to provide consent or obtain consent from a LAR
11. Unwilling or unable to use the OrthoCor Active System or Standard of Care (SOC) intervention
12. Unwilling or unable to complete the daily pain assessment
13. Enrolled in a study to evaluate an investigational drug
14. Prisoner or under incarceration

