9.5 Study Schedule of Assessments

In the evening of each day the subject should rate their pain using the provided scale and record their rating in the eDiary. Refer to Table 1 Schedule of Assessments.

Table 1. Schedule of Assessments

Assessments	Screening/Baseline (Day 0)	Day 1 - 14	Research Extension (if applicable) Day 15 – 30
Inclusion/Exclusion Criteria	X		
Demographics	X		
Surgical Date	X		
Pain Assessment	X	X	X
Self-reported Pre-Existing Conditions*	X*		
OrthoCor Active System/SOC Intervention Use		X	X
Device Information	X		
OrthoPod Information	X	X	X
Concomitant Pain Medication Use	X	X	X
Adverse Event, related to the test device		X	X
Pregnancy test for WOCBP	X		

* Information to be collected if available

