9. BLINDING

The study is not blinded.

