10. STUDY ASSESSMENTS

Mankoski Pain Scale assessments are conducted during the study for a period of 2 weeks of treatment with OrthoCor Active system or Standard of Care. The enrolled participant will have a treatment period from Day 0 through Day 14 when the study ends, and a research extension period and assessments are conducted for a period of additional 2 weeks (see Table 1. Schedule of Assessments in protocol).

The primary endpoints as well as safety analyses will be evaluated at study end.

Exploratory analyses will be assessed after the extension period of additional 2 weeks.

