12.1. Primary Endpoints

The primary endpoints of this study will be to compare the reduction of pain symptoms from baseline on the Mankoski Pain Scale after 2 weeks of treatment with the OrthoCor Active System device and Standard of Care.

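### SAP 12.9 does not count pain medication stopped during the 14 treatment days as concomitant, nor most or all of what is started after consent, although the protocol collects it

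*SAP*

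**What the plan says.** SAP 12.9 opens with a statement of scope: "All concomitant medication for pain will be recorded". It then defines the term: "A medication is considered concomitant if the start date is before the informed consent and there is no stop date", followed after a comma by "or the stop date is after the end of study treatment". The section ends there. It names no table, comparison by arm, covariate or sensitivity analysis, and no other part of the SAP uses the definition.

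The protocol uses the same term more broadly. Section 9.3 lists concomitant pain medication among the data to be collected. In Table 1 (section 9.5) the row "Concomitant Pain Medication Use" is marked at baseline, on Days 1-14 and in the extension. The protocol gives no definition by start and stop dates.

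Three other statements set the context:

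- The SAP gives a "treatment period from Day 0 through Day 14" (section 10) and states that "The study is not blinded" (section 9).
- The primary endpoint is to "compare the reduction of pain symptoms from baseline on the Mankoski Pain Scale after 2 weeks of treatment" (SAP 12.1). Protocol 9.5 has participants rate their own pain each evening.
- The only analgesics excluded by eligibility are opioids: "Current or expected use of opioids" (Protocol 8.5).

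**The concern.** A definition of concomitant medication should pick out what a participant took while on study. This one is built around medication that was already in use at consent and outlasted treatment. Such long-running background use is the kind least likely to change because of the assigned arm. A short course taken for a few days in the middle of the study, or a drug given up once pain eased, falls outside it.

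In this trial that matters for interpretation. Participants know their arm and rate their own pain, and they may use non-opioid analgesics. An effective analgesic would increase the reduction from baseline that the primary endpoint measures. If one arm started or stopped analgesics more than the other, a reader would want to see it beside the primary result. The SAP plans no adjustment or sensitivity analysis for analgesic use, so this section is the only place where it could appear.

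**Working it through.** The plan states no figure to reproduce here. The check applies the rule to possible start and stop dates.

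**Inputs.** Consent is taken as Day 0, the screening/baseline column of Table 1. Treatment ends on Day 14 (SAP 10). Let *s* be the start day and *e* the stop day.

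**Two readings of SAP 12.9.**

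- Strict (the start condition governs both clauses, the more natural reading): *s* < 0 and (no *e*, or *e* > 14).
- Loose (the clauses are independent): (*s* < 0 and no *e*), or *e* > 14.

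**Comparator.** Use that overlaps the period: *s* ≤ 14 and (no *e*, or *e* ≥ 0).

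| Example | Strict | Loose | Overlaps Days 0-14 |
|---|---|---|---|
| Started before consent, stopped Day 6 | no | no | yes |
| Started before consent, stopped Day 20 | yes | yes | yes |
| Started before consent, ongoing | yes | yes | yes |
| Started Day 3, stopped Day 10 | no | no | yes |
| Started Day 3, stopped Day 20 | no | yes | yes |
| Started Day 3, ongoing | no | no | yes |
| Started Day 16, stopped Day 20 | no | yes | no |

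**What follows.**

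1. *Stopped during treatment* (rows 1 and 4). Neither reading counts these. Row 1 has a stop date, so it fails the first clause, and 6 > 14 is false, so it fails the second. Row 4 fails for the same reasons with 10 in place of 6. A drug stopped on Day 14 itself also fails, because 14 > 14 is false.
2. *Started after consent* (rows 4 to 6). The strict reading counts none. The loose reading counts only row 5, where a stop date after Day 14 was recorded. Row 6 fails because it did not start before consent and has no stop date.
3. *The loose reading is not coherent.* It accepts a drug taken from Day 3 to Day 20 but rejects one taken from Day 3 onward without end. It also accepts row 7, which began after treatment was over.
4. *Against the protocol.* Table 1 collects pain medication use on Days 1-14. Rows 1, 4 and 6 all fall partly or wholly in that window, yet the SAP would not call them concomitant on either reading.

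Of the first six rows, the strict reading counts 2 and the loose reading 3. These are counts of patterns, not of patients, and they depend on how the categories are cut. Treating a start on the consent day and a stop on the last day as separate categories gives 3 × 4 = 12 overlapping patterns, of which 2 and 4 are counted. The fractions should not be read as the size of the problem.

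**The case against.** The strongest reply is that the damage is limited: the protocol still collects the information, no planned analysis depends on the definition, and SAP 13 says the SAP is based on the protocol. The first two parts stand. The third does not repair the rule, because the protocol has no date-based definition to fall back on and the SAP sentence is explicit.

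A reader might also infer more than the documents support:

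- *That every drug started after consent is left out.* This is true only on the strict reading. The loose reading admits those with a recorded stop date after treatment ends.
- *That a planned table is wrong, or that data are thrown away.* No table is specified, and Table 1 keeps the data. The fault lies in the classification.
- *That the definition makes device and analgesic effects inseparable.* A correct definition and a descriptive table would not separate them either. The documents also do not say what standard of care consists of. If it includes non-opioid analgesics, which they neither confirm nor exclude, that use is part of the comparator rather than a distortion of it. Actual use by arm would still need to be shown.
- *That the primary comparison is biased.* Nothing in the documents gives analgesic use in either arm, and the opioid exclusion narrows the scope.

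**Conclusion.** The definition is wrong as written, on either reading. It counts no pain medication stopped during the 14 treatment days. It counts none started after consent on the strict reading and, on the loose reading, only that with a recorded stop date after treatment ends. It conflicts with the data collection in Protocol 9.3 and Table 1, and nothing elsewhere in the SAP corrects it.

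The consequence is under-reporting of on-study non-opioid analgesic use in any summary that uses the definition, so a difference between arms could go unseen. How large that would be in patients or days of use cannot be computed from the documents. The primary test itself is unaffected. The conclusion assumes that consent falls on Day 0 and that the end of study treatment means Day 14, as SAP 10 implies. Its importance rests on the judgement that analgesic use matters for an unblinded, self-rated pain endpoint; the documents do not quantify this. It should be corrected before the analysis.

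**What to change.** Reword the definition in SAP 12.9 as follows:

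> A pain medication is concomitant if its start date is on or before the end of the 14-day treatment period and it has either no stop date or a stop date on or after the date of informed consent.

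This counts all six overlapping patterns in the table and rejects the seventh. Apply the same rule separately to the extension, using that period's own start and end, so that the two periods are not mixed.

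Add a descriptive summary by arm, with medications started after consent shown separately. Protocol 15.2 has the device reaching participants in 3 to 5 days, so in the device arm the summary should distinguish use before the device arrived from use after. The device-use details in Protocol 9.3 should supply that date; confirm that they do. Confirm also that the case report form holds start and stop dates, which the present SAP rule already presupposes.

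The cost is one reworded sentence and one new descriptive table from data the protocol already plans to collect. The table aids interpretation and does not itself separate a device effect from an analgesic effect.

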13. CHANGE FROM ANALYSES PLANNED IN THE PROTOCOL

This statistical analysis plan is based on protocol.
